### **Key Secondary Efficacy Endpoint #3, NPRS-AUC**

```
Proc mixed data=ADMI alpha=0.05;  
By _imputation_;  
Where PARAM="NPRS-AUC through Day 3 - MI" and AVISIT="Day 3";  
Class TRT01PN(ref='0') AGEGR2BL(ref='5 to 11  
years') NEUROBL(ref='No') COUNTRY(ref='India');  
model AVAL = TRT01PN SSSBL AGEGR2BL NEUROBL COUNTRY;  
lsmeans TRT01PN / cl pdiff;  
run;  
proc mianalyze data=Estimates alpha=0.05;  
modeleffects estimate;  
stderr StdErr;  
run;
```

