### **6.1.2. Adjustments for Covariates**

The comparison of the primary and secondary efficacy endpoints between the varespladib-methyl and placebo groups for the primary efficacy analysis will be adjusted for four variables: (1) baseline SSS composed of the pulmonary, cardiovascular, hematologic, renal, and nervous system sections treated as a continuous variable; (2) age group treated as a dichotomous variable (age 5-17 vs. age  $\geq$ 18 years); (3) baseline neurotoxicity (SSS neurological system subscore) treated as a dichotomous variable (0-1 vs.  $\geq$ 2); and (4) Country (U.S. vs. India). Because we anticipate low numbers of patients in the two pediatric age group strata, we have collapsed these two strata into a single group (age 5-17) for the purpose of data analysis. A sensitivity analysis for the primary and key secondary endpoints will include a fourth covariate: completion of the initial dose of antivenom prior to initiation of study drug (Yes or No).

The mixed model for repeated measurements (MMRM) will be adjusted for baseline SSS, baseline neurotoxicity, age group, completion of the initial dose of antivenom prior to initiation of study drug, and scheduled timepoint of assessment. It will also include terms for treatment-by-time interaction and baseline score-by-time interaction.

The Cox model to estimate the hazard ratios for all-cause mortality will be adjusted for baseline SSS, baseline neurotoxicity, age group, and completion of the initial dose of antivenom prior to initiation of study drug.

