### 8.1.2. Key Secondary Efficacy Endpoints

The ITT population will be used to analyze the secondary efficacy endpoints. All secondary endpoints will be analyzed using the prespecified assessment timepoints according to the protocol. All statistical models for change from baseline in a particular endpoint will include covariates for baseline value of the particular endpoint, baseline SSS, baseline neurotoxicity (Yes, No; based on the SSS neurological system subscore), age group (5-17, 18+), and country (U.S. vs. India). Key secondary endpoints will be tested sequentially using a fixed-sequence gatekeeping procedure for the hierarchical testing of multiple endpoints. The significance of the treatment effect for the primary endpoint (i.e., change in SSS from baseline to average at 6 and 9 hours) will be the first hypothesis tested, using a significance level of 0.05. If the null hypothesis for the primary endpoint is rejected, then the first key secondary endpoint (i.e., AUC of SSS through Day 7) will be tested, also with a significance level of 0.05. If the null hypothesis for this test is rejected, the second key secondary endpoint (total antivenom use) will be tested ( $\alpha=0.05$ ).

If the null hypothesis for this test is rejected, the third key secondary endpoint (AUC of NPRS through Day 3) will be tested ( $\alpha=0.05$ ). If the null hypothesis for this test is rejected, the fourth key secondary endpoint (CGI-I at Day 2) will be tested ( $\alpha=0.05$ ). Sensitivity and subgroups analyses of the primary and key secondary endpoints will not be part of the gatekeeping procedure for hierarchical testing of endpoints.

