### **8.1.2.3. AUC of the NPRS from Baseline Through Day 3**

An ANOCVA will be used to compare the NPRS-AUC3d for the two treatment groups with baseline NPRS score, age group (5 to 17 years,  $\geq$  18 years), baseline neurotoxicity, and country as covariates. The comparison of varespladib-methyl to placebo (varespladib-methyl vs. placebo) will be tested at a 5% two-sided significance level; the corresponding 95% two-sided confidence interval will be presented. The AUC will be calculated according to [Section 6.1.7.3](#). A reduction in NPRS-AUC (i.e., negative parameter estimate) will represent a faster average improvement in pain symptoms. Subgroup analyses will estimate the treatment effect separately for pediatric and adult patients, for patients with and without clinically significant neurotoxicity, for patient who have and have not completed an initial dose of antivenom prior to randomization, for the U.S. and for India, for each snake type (viper, elapid, and unknown), and for patients for whom the time from bite or symptom onset to receipt of study drug was <5 hours and  $\geq$ 5 hours.

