### **8.1.2.4. Clinical Global Impression – Improvement (CGI-I) at Day 2**

CGI-I (1-7 scale) at Day 2 will be treated as a continuous variable with scores compared using ANCOVA, with treatment as the variable of interest, and with baseline SSS, age group, baseline CGI-I score, baseline neurotoxicity, and country as covariates. The model will be used to estimate the effect of treatment on CGI-I scores at Day 2. The comparison of varespladib-methyl to placebo (varespladib-methyl vs. placebo) will be tested at a 5% two-sided significance level;

the corresponding p-value and 95% two-sided confidence intervals will be presented.

A sensitivity analysis will add completion of initial dose of antivenom prior to initiation of study drug as a covariate. Subgroup analyses will estimate the treatment effect separately for pediatric and adult patients, for patients with and without clinically significant neurotoxicity, for patient who have and have not completed an initial dose of antivenom prior to randomization, for the U.S. and for India, for each snake type (viper, elapid, and unknown), and for patients for whom the time from bite or symptom onset to receipt of study drug was <5 hours and  $\geq 5$  hours.

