### **Key Secondary Efficacy Endpoint #4, CGI-I**

```
Proc mixed data=ADMI alpha=0.05;  
Where PARAM="CGI-I Score" and AVISIT="Day 2";  
Class TRT01PN(ref='0') AGEGR2BL(ref='5 to 11 years')  
NEUROBL(ref='No') COUNTRY(ref='India');  
Model AVAL = TRT01PN SSSBL AGEGR2BL NEUROBL COUNTRY;  
lsmeans TRT01PN / cl pdiff;  
run;  
proc mianalyze data=Estimates alpha=0.05;  
modeleffects estimate;  
stderr StdErr;  
run;
```

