#### **8.2.6. NPRS Score in Subjects Able to Respond from Baseline through Day 28**

The absolute values and change of NPRS will be tabulated by treatment arm and visit. An MMRM approach as described in [Section 8.2.1](#) will be used to assess the treatment effect on NPRS scores through Day 28. The MMRM will include the fixed effect of treatment as the variable of interest, with the baseline NPRS, baseline SSS, age group, baseline neurotoxicity, and visit, and visit by treatment interaction as covariates.

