### **8.2.13. Clinical Global Impression–Improvement (CGI-I) from Baseline through Day 7**

CGI-I (1-7 scale) will be treated as a continuous variable and summary statistics will be reported at each visit and depicted graphically showing mean scores for each treatment group over time. CGI-I scores from baseline through day 7 will be compared using MMRM, with treatment as the variable of interest, with baseline SSS, age group, baseline CGI-I score, and baseline neurotoxicity as covariates. The model will be used to estimate the effect of treatment on CGI-I scores at each assessment time point through Day 7.

Secondarily, CGI-C will be dichotomized into subjects who are responders (score of either 1 – very much improved; 2 – much improved) vs. non-responders (scores of 3-7). The proportion of responders within each treatment group will be compared with logistic regression including the same covariates described above.

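### SAP text and sample code name different baseline covariates for two alpha-protected tests (NPRS-AUC and CGI-I at Day 2), so the planned models cannot be identified

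*SAP*

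**What the plan says.** SAP 2.2.1.2 and 8.1.2 place NPRS-AUC third and CGI-I at Day 2 fourth among the key secondary endpoints. Each is tested at 0.05 only if every earlier null, starting with the primary, has been rejected.

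**NPRS-AUC.** Section 8.1.2.3 specifies an ANCOVA "for the two treatment groups with baseline NPRS score, age group (5 to 17 years" and over), baseline neurotoxicity and country. Baseline SSS is not in the list. The code for this endpoint in 8.1.3 reads "model AVAL = TRT01PN SSSBL AGEGR2BL NEUROBL COUNTRY", which has baseline SSS and no NPRS term.

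**CGI-I at Day 2.** Section 8.1.2.4 specifies an ANCOVA "with baseline SSS, age group, baseline CGI-I score, baseline neurotoxicity, and country as covariates". The code reads "Model AVAL = TRT01PN SSSBL AGEGR2BL NEUROBL COUNTRY", with no baseline CGI-I term.

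**General rules.** Section 6.1.2 covers the primary and secondary endpoints. It names age group, baseline neurotoxicity, country and "baseline SSS composed of the pulmonary, cardiovascular, hematologic, renal, and nervous system sections treated as a continuous variable", with no endpoint-specific baseline. Section 8.1.2 says: "All statistical models for change from baseline in a particular endpoint will include covariates for baseline value of the particular endpoint, baseline SSS", followed by neurotoxicity, age group and country.

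**Neighbouring analyses.** The NPRS repeated-measures model in 8.2.6 is fitted "with the baseline NPRS, baseline SSS, age group, baseline neurotoxicity, and visit, and visit by treatment interaction as covariates". The CGI-I repeated-measures model in 8.2.13 is fitted "with baseline SSS, age group, baseline CGI-I score, and baseline neurotoxicity as covariates".

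Section 8.1.3 describes its code as sample code for these analyses. No sentence says whether text or code prevails.

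**The concern.** SAP 4.1 calls the study confirmatory and its tests formal. Section 1 calls the SAP an a priori plan, to be approved before unblinding. For these two tests the approved plan would not determine the model, and so would not determine the p-value. A programmer who follows 8.1.3 as printed would leave out a baseline score that the endpoint-specific section requires and that the trial already schedules. What is at stake is mainly the precision of the NPRS-AUC comparison, and then the ability of an outside reader to tell which analysis was planned.

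**Working it through.** **1. Lists side by side (baseline scores only; neurotoxicity, age group and country are common to all rows).**

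| Place in SAP | Baseline SSS | Endpoint baseline |
|---|---|---|
| 6.1.2, general | yes | no |
| 8.1.2, general, worded for change from baseline | yes | yes |
| 8.1.2.3, NPRS-AUC text | no | yes (NPRS) |
| 8.1.3, NPRS-AUC code | yes | no |
| 8.1.2.4, CGI-I text | yes | yes (CGI-I) |
| 8.1.3, CGI-I code | yes | no |

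For NPRS-AUC the SAP supports three baseline sets: SSS alone, NPRS alone, or both. The general rule in 8.1.2 does not settle it, because the outcome is an AUC and both code blocks model `AVAL`, not change. For CGI-I there are two sets, with or without baseline CGI-I.

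**2. The plan's own figure.** Section 3.2 states 94 patients, 85% power, difference 1.1 and SD 1.75 for the primary endpoint. The two-sample t calculation gives 46.43, so 47 per arm and 94 in total, with power 85.4%. The figure reproduces and does not depend on this point. The documents give no power for NPRS-AUC or CGI-I and no correlations, so the sizes below are illustrations.

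**3. Leaving a baseline out of a model that already has SSS.** If the omitted baseline has partial correlation r with the outcome given SSS, the standard error is multiplied by 1/√(1 − r²):
- r = 0.2: 1/√0.96 = 1.021
- r = 0.3: 1/√0.91 = 1.048
- r = 0.5: 1/√0.75 = 1.155

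For a test with an assumed 80% power in the fuller model, power becomes Φ[(1.960 + 0.842)·√(1 − r²) − 1.960], which is 78%, 76% and 68%.

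**4. Using SSS instead of NPRS (code against 8.1.2.3).** Let rN and rS be the correlations of baseline NPRS and baseline SSS with NPRS-AUC. The standard error factor for code relative to text is √[(1 − rS²)/(1 − rN²)]:

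| | rS = 0 | rS = 0.2 |
|---|---|---|
| rN = 0.2 | 1.021 | 1.000 |
| rN = 0.3 | 1.048 | 1.027 |
| rN = 0.5 | 1.155 | 1.131 |

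The factor is 1 whenever rS = rN, and below 1 if SSS is the better predictor.

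**5. Is a high rN built in?** Only slightly. SAP 6.1.7.3 includes the baseline score in an AUC over 48 hours. The first post-dose assessment is at 3 to 4 hours, so the trapezoid weight of the baseline score is between (3/2)/48 = 3.1% and (4/2)/48 = 4.2%. The gain therefore depends on how far pain persists from baseline, which the documents do not say.

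**6. Degrees of freedom.** Intercept, treatment, one baseline, age group, neurotoxicity and country make six parameters, leaving 94 − 6 = 88. A second baseline leaves 87.

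**The case against.** **The code is only illustrative.** It is called sample code, and the SAP sends the reader to 8.1.2 for the details. It also has other slips. The CGI-I block has no `BY _imputation_` line although it feeds PROC MIANALYZE, and the treatment reference level is '0' in the NPRS-AUC block but '2' in the antivenom block. A drafting error is the likeliest explanation. This largely answers the CGI-I case, where 8.1.2.4 and 8.1.2 both include baseline CGI-I. It does not answer NPRS-AUC, because 6.1.2, 8.1.2 and 8.1.2.3 disagree with each other before the code is considered.

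**Type I error.** A reader might infer that the open choice inflates the trial's error rate. If the text or code model for NPRS-AUC were picked after seeing both results, its local error would be about 5.9 to 6.6% (rN = 0.2 to 0.3) or 7.1 to 7.4% (rN = 0.5). Those figures come from simulation with 47 or 55 per arm, rS of 0 or 0.2, and an SSS-NPRS correlation of 0.2. The documents do not support that reading. Section 1 makes the plan a priori and requires post-hoc work to be labelled, section 10 says that changes were made blind and before database lock, and no passage permits a choice after unblinding. NPRS-AUC is tested only after three earlier rejections, so familywise error is unchanged under the global null. Even with such a choice, familywise error would pass 5% only if those three nulls were all rejected with probability above about 67 to 85% (5/7.4 to 5/5.9, treating the tests as independent).

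**Baseline CGI-I is not a clean pre-dose covariate.** Protocol 10.2.2 lets it be recorded after study drug has started, and SAP 6.1.1 accepts baseline values taken immediately after the first dose. It is also rated against previous status, whereas later ratings are made against baseline. This stands: the CGI-I mismatch could reasonably be resolved either way.

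**SSS-AUC.** A reader might extend the point to this endpoint. Its text and code covariate lists agree. Whether its baseline SSS has five or six sections, and how the parameter is labelled, are drafting matters outside this point.

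**Conclusion.** The conflict is real for both endpoints and should be removed before unblinding, but its impact is limited. For NPRS-AUC, the code leaves out the baseline score that the endpoint's own section requires. Relative to a model with both baselines, this enlarges the standard error by 2%, 5% or 15% under assumed partial correlations of 0.2, 0.3 or 0.5. Relative to the model in 8.1.2.3, the loss is nil if SSS predicts pain as well as baseline NPRS does. The second cost is that the planned model cannot be read from the document. For CGI-I the precision loss is probably small, and the test is last in the sequence, so its result blocks nothing. Any single model named in advance is valid at 5%. The inconsistency itself rests on the documents alone; every size given rests on assumed correlations.

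**What to change.** Before unblinding:

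1. **NPRS-AUC.** Add baseline NPRS to the MODEL statement in 8.1.3. Make 6.1.2, 8.1.2, 8.1.2.3 and 8.1.3 state one list, saying whether baseline SSS is also included. Section 8.2.6 already uses both.
2. **CGI-I at Day 2.** Make 8.1.2.4 and the code agree on one model. If baseline CGI-I is kept, either restrict it to ratings made before the first dose or justify using ratings made after it.
3. **Age group, as a separate correction.** Section 8.1.3 defines `AGEGR2BL` as 5 to 11 against 12 to 17 years, and the code for the primary, SSS-AUC, NPRS-AUC and CGI-I uses '5 to 11 years' as the reference level. Change the definition and these reference levels to 5 to 17 against 18 and over, as in 6.1.2. A rule that text governs over code would not settle this, because the 8.1.3 definition is itself SAP text.

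The cost is a few lines of text and code. No degree of freedom is lost if baseline NPRS replaces baseline SSS, and one of about 88 is lost in any model that gains a baseline. Both baseline scores are already scheduled, so no new data are needed.

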### **Key Secondary Efficacy Endpoint #4, CGI-I**

```
Proc mixed data=ADMI alpha=0.05;  
Where PARAM="CGI-I Score" and AVISIT="Day 2";  
Class TRT01PN(ref='0') AGEGR2BL(ref='5 to 11 years')  
NEUROBL(ref='No') COUNTRY(ref='India');  
Model AVAL = TRT01PN SSSBL AGEGR2BL NEUROBL COUNTRY;  
lsmeans TRT01PN / cl pdiff;  
run;  
proc mianalyze data=Estimates alpha=0.05;  
modeleffects estimate;  
stderr StdErr;  
run;
```

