#### 6.1.4.1. Multiple Imputation

The multiple imputation (MI) procedures for the primary and key secondary endpoints are described below.

For the primary analysis, missing data not due to mortality, and not addressed by the averaging rules above, will be imputed using the following regression-based multiple imputation model.

The following imputation algorithm will be applied to each SSS subscore separately, then the primary outcome SSS score will be derived.

1. The first step is to understand the pattern of missingness. In order to perform the multiple imputation, a monotone missing pattern must be achieved. For example, if there exist values for baseline and Day 2 visits, but missing values for the Day 1 (8-10h) visit, Markov-Chain Monte-Carlo (MCMC) method will be used to impute the small amount of missing data that may be missing at the intermediate visits that is required to make the missing data pattern monotone before applying the multiple imputation algorithm. This method uses a non-informative Jeffreys prior to derive the posterior mode from the expectation-maximization (EM) algorithm as the starting values for the MCMC method. This MCMC method will use seed of 432832. To avoid values that could not be observed in practice, imputed values will be constrained to be integers in the range of 0 to 3 or 0 to 4 by convention to align with the scale of the questionnaire. A total of 10 imputations will be done in the MCMC step.
2. Once the monotone pattern is achieved, the next step is to implement the imputation algorithm. For this, the Predictive Mean Matching method (PMM) will be used. This method is particularly helpful if the normality assumption is violated. For subjects with complete data up to a particular visit, a PMM model will be fit that includes the outcome at that visit as the dependent variable; and as independent variables gender, treatment assignment, study site, and non-missing scores using a seed of 931428. This process will be repeated 15 times, resulting in a total of 150 complete analysis datasets.
3. For each completed dataset, any necessary derived variables will be computed. Then the ANCOVA model will be performed for the 6 and 9 hour average SSS score. The results will be combined into one MI inference (LS mean, associated 95% CI, and p-value) using PROC MIANALZE as illustrated (Ratitch et al., 2013).

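### The sample code for CGI-I at Day 2 does not carry out the analysis that the SAP text specifies: it drops the baseline CGI-I covariate and fits the imputed data without a BY statement

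*SAP*

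**What the plan says.** SAP Section 8.1.2.4 treats Day 2 CGI-I as continuous and compares the arms by ANCOVA with "baseline SSS, age group, baseline CGI-I score, baseline neurotoxicity, and country as covariates", at the two-sided 5% level. Sections 2.2.1.2 and 8.1.2 make it the fourth and last key secondary endpoint in the fixed sequence.

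Section 6.1.4 handles missing CGI-I by multiple imputation, and Section 6.1.4.1 applies the method of the primary endpoint. That method has ten MCMC imputations and 15 predictive-mean-matching repeats, "resulting in a total of 150 complete analysis datasets". An ANCOVA follows in each dataset, and the results are pooled.

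Section 8.1.3 gives code that it labels as sample code. The block for key secondary endpoint #4 reads the imputed file `ADMI`, filters it with "Where PARAM='CGI-I Score' and AVISIT='Day 2", fits "Model AVAL = TRT01PN SSSBL AGEGR2BL NEUROBL COUNTRY" and then calls `PROC MIANALYZE`. It has no BY statement. The blocks for the primary endpoint, SSS-AUC and NPRS-AUC each have "By _imputation" (the variable is `_imputation_`).

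Section 6.1.2 says in general terms that the primary and secondary comparisons "will be adjusted for four variables": baseline SSS, age group, baseline neurotoxicity and country.

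**The concern.** An alpha-protected test should have one specification, and the printed code should be able to produce it. Here the code departs from the endpoint text in two ways.

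The missing covariate is silent. The procedure converges and returns a plausible p-value, so nothing prompts the programmer to check Section 8.1.2.4. The general list in Section 6.1.2 happens to match the code, which makes the slip harder to see. The MODEL line also looks copied: the NPRS-AUC block has the same one, "model AVAL = TRT01PN SSSBL AGEGR2BL NEUROBL COUNTRY", although Section 8.1.2.3 compares NPRS-AUC "for the two treatment groups with baseline NPRS score, age group" and the other factors.

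The missing BY statement is a different kind of error. The block analyses all completed datasets in one fit and then asks for pooling, so it contradicts itself.

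**Working it through.** **1. Covariates side by side (besides treatment).**

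| SAP source | Covariates |
|---|---|
| 8.1.2.4, CGI-I text | baseline SSS, age group, **baseline CGI-I**, neurotoxicity, country |
| 8.1.3, code #4 | baseline SSS, age group, neurotoxicity, country |
| 6.1.2, general list | baseline SSS, age group, neurotoxicity, country |
| 8.1.2, rule for change-from-baseline models | **baseline value of the endpoint**, baseline SSS, neurotoxicity, age group, country |

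The endpoint-specific text names the term. Section 8.1.2 points the same way, although its wording covers change-from-baseline models and the code analyses the score itself. Section 8.1.2.2 shows that endpoint sections extend the general list, since it adds prior antivenom.

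**2. Number of datasets.** 10 × 15 = 150, which reproduces the SAP figure.

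**3. Cost of the missing covariate.** Let r be the partial correlation between baseline and Day 2 CGI-I. The documents give none, so r = 0.1, 0.3 and 0.5 are assumptions. The code model has 6 parameters and the text model has 7. The ratio of standard errors, code to text, is

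[1/√(1 − r²)] / √(1 + 1/(N − 8)).

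- N = 94: 1.005/1.0058 = 0.999; 1.048/1.0058 = 1.042; 1.155/1.0058 = 1.148.
- N = 110: 1.000, 1.043, 1.149.

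If the text model is assumed to have 80% power (the SAP does not power this endpoint), the code model has 80%, 77% and 68% at N = 94 or 110, from the noncentral t. In 10,000 simulated complete-data trials per setting at N = 94, the two models disagreed on significance in 2.9%, 7.5% and 17.0% of trials at that effect, and in 1.0%, 2.9% and 4.7% with no effect. Each model alone rejected a true null in 4.8% to 5.3% of trials.

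**4. The missing BY statement.** Fitted once to 150 stacked copies, with few values imputed, the standard error is too small by √[(150N − 6)/(N − 6)]:

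- N = 94: √(14,094/88) = 12.66.
- N = 110: √(16,494/104) = 12.59.

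That is an intermediate quantity. Pooling needs the between-imputation variance, which divides by m − 1. One fit gives m = 1 estimate of the treatment difference, so m − 1 = 0 and there is no pooled result.

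**5. Whether copying the BY line is enough.** In Section 6.1.4.2, Step 2 runs by `_imputation1_` with 15 imputations, so `_imputation_` would run from 1 to 15 within each of ten groups. BY processing on `_imputation_` alone would give 15 fits, each on 10 stacked copies, with a within-imputation standard error too small by about √[(10 × 94 − 7)/(94 − 7)] = √(933/87) = 3.3. This does not arise if an unprinted step builds a combined index from 1 to 150.

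**6. Age coding in the same block.** Section 8.1.3 describes `AGEGR2BL` as two pediatric bands (5 to 11 and 12 to 17 years), and the CGI-I block uses the younger band as reference. Sections 6.1.2 and 8.1.2 group age as 5–17 against 18 and over. The antivenom block already uses 5 to 17 years as reference.

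**The case against.** The strongest reply is that the prose is clear and the code is only a sample. Section 8.1.2.4 names baseline CGI-I, and Sections 6.1.4 and 6.1.4.1 leave no doubt about fitting per dataset and pooling. The blocks are also schematic: none prints the step that creates the `Estimates` file passed to `PROC MIANALYZE`. All of this stands. It means the fault lies mainly between code and prose. A reader might infer that the SAP prespecifies two rival models of equal standing. The documents do not support that, because the specific text governs and the general list is extended elsewhere.

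A reader might also infer a grossly inflated false-positive rate. Simulation puts it near 87% if the p-value from the stacked fit were read directly. But the plan calls for pooling, the block calls the pooling procedure, and no pooled result would emerge. The 12.66-fold factor therefore reaches no reported conclusion.

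The size of the covariate effect is also fairly challenged. Under Protocol Section 10.3.1.2, baseline CGI-I is rated against previous status and later ratings against baseline. The reference points differ, so nothing anchors r = 0.5.

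The reply does not remove the need to correct the code. The SAP's document history shows that code for the primary and key secondary endpoints was added on purpose, and Section 4.1 calls the study confirmatory.

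**Conclusion.** The code for CGI-I at Day 2 does not implement the SAP text, and it should be fixed. The covariate omission matters more because it is silent. It introduces no bias, the 5% level holds, and the loss of precision runs from about none (r = 0.1) to a standard error about 15% larger (r = 0.5), on an assumed range. The missing BY statement stops the block from giving the planned inference but would probably be noticed when run. Because CGI-I is tested last, neither slip affects another test.

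One minor item goes with this. The imputation code sets a lower bound of 0, whereas CGI-I runs from 1 to 7 and a 0 on the form in Protocol Appendix C1 marks an assessment not done. A reader might infer that impossible scores will enter the analysis. The documents do not show this: the code is a generic template, and Section 6.1.4.1 describes its bounds for the SSS subscores.

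**What to change.** Before database lock:

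- In the CGI-I block, add the baseline CGI-I term to the MODEL line.
- Add BY processing on one index that identifies all 150 datasets, built from `_imputation1_` and `_imputation_`. Use the same index in the primary, SSS-AUC and NPRS-AUC blocks.
- Correct the `AGEGR2BL` definition and levels throughout Section 8.1.3 to 5–17 against 18 and over.
- State in Section 6.1.2 that endpoint-specific covariate lists override the general four, and add baseline NPRS to the NPRS-AUC code to match Section 8.1.2.3.
- Set the CGI-I imputation bounds to 1 and 7, and treat a recorded 0 as missing.

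If baseline CGI-I is not wanted, amend Section 8.1.2.4 instead, before unblinding. The cost is a few lines of code and one sentence, with no new data and no change of method.
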